2.5 Statistical evaluation

A McNemar test will be applied to the B-mode ultrasound alone and B-mode ultrasound with additional ultrasonographic examinations positive and negative results to determine statistical independence. ROC analysis will be performed to estimate the overall performance of B-mode ultrasound and multiparametric ultrasound. Using the histopathological data the numbers of true-negative (TN), true-positive (TP), false-negative (FN) and false-positive (FP) results for B-mode ultrasound and multiparametric US will be obtained and sensitivity, specificity, accuracy, positive predictive value (PPV) and negative predictive value (NVP) for both methods will be calculated.

3. Timetable

September 2015	Obtaining IRB approval
September 2015 to April 2017	Multiparametric ultrasound examinations according to protocol
May/June 2017	Statistical evaluation
July to September 2017	Preparation and submission of manuscripts

AMENDMENT TO THE STUDY PROTOCOL

Treatment of early breast cancer is usually surgical, comprising breast-conserving surgery for small, unifocal tumors, or mastectomy for larger or multicentric tumors. However, in women with locally aggressive disease or whose tumors display features that are predictive of early recurrence, neoadjuvant chemotherapy (NAC) is given to reduce the risk of recurrence. The early identification of chemotherapy responders and non-responders is crucial

in order to allow chemotherapy scheme modifications or changes to surgery or hormonal therapy, and thus provide optimal patient outcomes. Yet tumor response to NAC can be very different, resulting in fibrosis, concentric shrinking, fragmentation or change in the density of malignant tissue. All of these may affect the evaluation of residual tumor size (28).

Evaluation of tumor response to NAC is routinely done by using solely morphologic criteria (size reduction in mammography or B-mode ultrasound (US)), with US being more accurate than mammography in the evaluation of residual tumor size after NAC (28), showing a moderate correlation with the final histopathologic tumor size (29).

However, the potentials of a multiparametric (mp) US have not yet been explored. We hypothesize that a functional imaging of the breast using high-resolution mp US allows an improved monitoring of therapy-induced changes before morphologic changes are visible (e.g. tumor-shrinkage). Our approach focuses on the assessment of specific imaging biomarkers, which help to differentiate treatment responders from non-responders immediately after onset of NAC. The aim of this study-phase is to acquire mp US data with CP/PD, elastography and CEUS for an improved assessment of early treatment response.

For this reason, 40 patients with breast cancer undergoing NAC will be imaged before, during and after NAC/pre-surgery with mp US imaging of the breast. This number of patients is necessary for a hypothesized improvement of the AUC by 20% (from 0.7 to 0.9) with a type I error of 5% and a type II error of 20%. The participants to this part of the study will be recruited among the patients, already taking part in the first part of the study and planned to receive a NAC, according to the recommendations of the interdisciplinary tumor board. Due to different underlying biochemical processes of the different US modalities, it can be assumed that the single modalities may have different time frames for the early detection of therapy-induced changes- yet literature data on this subject are sparse. To monitor therapy response, the patients will receive a baseline mp US examination (as already planned in the study protocol) and an additional mp US examinations on the 3rd day after the 1st cycle, in order to evaluate possible initial changes in tumor morphologic and functional parameters, induced by NAC, which might allow for an early

prediction of histologic response. Patients will be examined again in the week after the 2nd, 4th and 6th (last) cycles of NAC. In cases where 8 NAC cycles will be necessary, a further examination will be planned after the 8th cycle.

The image analysis will be conducted as described in the original study protocol.

Qualitative and quantitative imaging parameters will be correlated with histopathological tumor grade, microvascular density as an indicator of tumor-neoangiogenesis, hormone receptor status and other newer factors such as HER2-neu proliferative indices and gene expression profile before and after NAC.

For the assessment of treatment response, functional imaging data of the baseline examination and of the examinations after the 1st, 2nd, 4th and 6th (+/- 8th) cycle will be compared for therapy-induced changes of both lesion morphology and functional capabilities by two experienced radiologists independently.

The statistical evaluation will be performed as described in the original study protocol.

CHANGES IN THE STUDY PROTOCOL

- Additional mp US examinations after the first, second, fourth and sixth (and after the eighth, if 8 NAC cycles are necessary) cycle of NAC.
- Correlation of qualitative and quantitative imaging parameters with histopathological tumor grade, microvascular density, hormone receptor status, HER2-neu, proliferative indices and gene expression profile before and after NAC.

4. Literature

2. Stavros AT. Breast ultrasound. Philadelphia: Lippincott, Williams and Wilkins; 2004.

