1.2 Clinical perspective and study aim

In this prospective study we will perform multiparametric high resolution ultrasound in patients with known suspicious breast lesions (BI-RADS 4 and 5). We will acquire morphologic by conventional B-mode and 3D US and functional information about the lesions by examination of tumor vascularity and structure as expressed by means of stiffness. It can be expected that with this multiparametric US imaging an increased sensitivity and especially specificity of US of the breast can be achieved.

2. Patients and Methods

Over a period of 24 months 120 patients with breast lesions categorized as BI-RADS 4 and 5 (3) will be included in this prospective study- that means patients with suspicious lesions, planned to undergo an image-guided biopsy or surgery. This number of patients is necessary for a hypothesized improvement of the AUC by 10% (from 0.8 to 0.9) with a type I error of 5% and a type II error of 20%. The recruitment of patients will take place immediately after a breast clinical or imaging examination (mammography, ultrasound or MRI of the breast) demonstrating a suspicious breast lesion as described previously. All patients will be examined with multiparametric ultrasound. Contrast-enhanced examination will be conducted subsequently to the non contrast-enhanced one. The whole examination time will be approximately 30 minutes. Histopathology with either image-guided biopsy or surgery will be used as the standard of reference. Both in situ and invasive carcinomas will be regarded as a malignant (positive) result whereas benign and precursor lesions will be regarded as a benign (negative) result. In case of an image-guided biopsy, this will be performed immediately after the sonographic examination, whereas in the cases of planned surgery, this will be performed according to the planning of the respective Departments of Surgery or Gynecology.

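### The only named test, an unsplit McNemar test, compares positive-call rates, and the AUC difference that sized both study parts has no test or interval

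*Combined protocol and SAP*

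**What the plan says.** Section 2.5 is the whole statistical plan for the first part of the study. Its first sentence reads "A McNemar test will be applied to the B-mode ultrasound alone and B-mode ultrasound with additional ultrasonographic examinations positive and negative results", and the stated purpose concerns "positive and negative results to determine statistical independence". The second sentence says "ROC analysis will be performed to estimate the overall performance of B-mode ultrasound and multiparametric ultrasound". Histology enters only in the third: "Using the histopathological data the numbers of true-negative (TN), true-positive (TP), false-negative (FN) and false-positive (FP) results for B-mode ultrasound and multiparametric US" are to be obtained, and sensitivity, specificity, accuracy and predictive values calculated from them. No test or confidence interval is named for a difference in AUC, sensitivity or specificity.

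The sample size in section 2 (Patients and Methods) rests on the AUC: "This number of patients is necessary for a hypothesized improvement of the AUC by 10% (from 0.8 to 0.9", with 5% type I and 20% type II error. The aim in section 1.2 is that "an increased sensitivity and especially specificity of US of the breast can be achieved".

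The amendment sizes its 40 chemotherapy patients in the same way: "This number of patients is necessary for a hypothesized improvement of the AUC by 20% (from 0.7 to 0.9", with the same error rates. For analysis it refers back: "The statistical evaluation will be performed as described in the original study protocol".

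**The concern.** A McNemar test on all paired positive/negative calls tests equality of the two marginal positive-call rates. It does not test independence, so the stated purpose is wrong, and it does not test accuracy unless the calls are split by histology or recoded as correct/incorrect. Section 2.5 does neither.

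Three things are at stake. The test can miss an improvement in both sensitivity and specificity, because they move the positive-call rate in opposite directions. It can be significant when only the threshold has moved, or when sensitivity has fallen. And the hypothesis to which the 5% and 20% error rates belong, the AUC difference, is never tested. Sensitivity and specificity would be reported alongside, so a loss would be visible, but without a test or interval for either difference.

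**Working it through.** **1. The plan's own sample sizes.** The documents give the AUCs and error rates, but not the malignant (or responder) share, the correlation, the sidedness or the method, so 120 and 40 cannot be reproduced from them alone. Both are attainable. For a two-sided paired comparison with Hanley–McNeil variances, 60% positive and correlation 0.5 between the AUC estimates (all assumed), the requirement is (1.960 + 0.842) × SE ≤ AUC difference, with SE² = v1 + v2 − 2r√(v1·v2). At N=117 (70 positive, 47 negative), v1 = 0.001602 for AUC 0.8 and v2 = 0.000795 for AUC 0.9. Hence SE² = 0.001268, SE = 0.0356 and 2.802 × 0.0356 = 0.0998 ≤ 0.1. The same setting gives 41 for 0.7 v 0.9. Over positive shares 0.3–0.7 and correlations 0–0.7 the formula gives 76–338 and 29–102. A single AUC against a fixed value, also two-sided with 60% positive, gives 123 and 42. The sample sizes are not shown to be wrong.

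**2. What the unsplit test compares.** With prevalence π of malignancy:

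change in positive-call rate = π × (gain in sensitivity) − (1 − π) × (gain in specificity).

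This is algebra and needs no distributional assumption.

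**3. Count example** (60 malignant, 60 benign, assumed). Sensitivity and specificity both rise from 43/60 to 49/60. Correct calls go from 43 + 43 = 86 to 49 + 49 = 98. Positive calls are 43 + 17 = 60 before and 49 + 11 = 60 after. The discordant counts are therefore equal and the exact p is 1.0.

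**4. Rejection rates, N=120.** Assumed: π 0.3–0.7, correlation r 0.3–0.7 between latent scores within each histology group, equal-variance binormal scores, exact two-sided McNemar at 5%, power by enumeration. Separation d = √2 × z(AUC), which is 1.190 for AUC 0.8 and 1.812 for 0.9; specificity = Φ(d − z(sensitivity)).

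One cell in full: π = 0.5, r = 0.5, sensitivity held at 90%, so specificity goes from 46.4% to 70.2%. In malignant lesions, 6.76% change call in each direction. In benign lesions, 30.66% change from positive to negative and 6.80% the other way. Pooled, the discordant proportions are 0.5 × 0.0676 + 0.5 × 0.0680 = 0.0678 and 0.5 × 0.0676 + 0.5 × 0.3066 = 0.1871. Power is 69% pooled, against 85% for McNemar in the 60 benign lesions alone.

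Ranges over the grid:

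| Scenario | McNemar, all calls | McNemar, benign only |
|---|---|---|
| AUC 0.8→0.9, symmetric (Se = Sp 72%→82%) | 3–10% | 10–40% |
| AUC 0.8→0.9, Se 90%→94.5%, Sp 46%→59% | 3–31% | 14–50% |
| AUC 0.8→0.9, Se 90% fixed, Sp 46%→70% | 29–96% | 52–98% |
| AUC 0.8→0.9, Se 94.5% fixed, Sp 34%→59% | 36–97% | 53–99% |
| AUC 0.8 for both, cut-off moved 0.4 SD (Se 72%→84%, Sp 72%→58%) | 63–85% | not applicable |
| Se 95%→75%, Sp 85% unchanged (illustration) | 21–95% | not applicable |

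In the four planned-gain rows the benign-only test has higher power than the pooled test in every cell.

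**5. A paired AUC test in the same model.** DeLong on the continuous score, simulated, rejects in 57–66% at r=0.3, 69–77% at r=0.5 and 87–93% at r=0.7 for AUC 0.8 v 0.9. With no AUC gain it rejects in 5–6%. With ordinal ratings at r=0.5 it rejects in 64–71% (four categories) or 67–75% (six).

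No rejection rate is given for the 40-patient part, because the amendment defines no positive/negative response call.

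**The case against.** The strongest reply is that section 2.5 is terse rather than wrong. It is silent on strata, and the same paragraph obtains true and false positives and negatives for both methods, so McNemar by histology or on correct/incorrect calls may have been meant. ROC analysis of both methods is planned, section 2.4 says their results will be compared, and the sample-size statement implies an AUC test. On this view one clarifying sentence would be enough.

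Part of this stands. The intention may have been sound, and a comparison is clearly intended. But the sentence gives no split, and an analyst following it literally would run the pooled test. Even with a split, the AUC difference would have no named test or interval.

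The size is also conditional. Exact cancellation requires the gains to balance, and section 1.2 stresses specificity. If sensitivity is held at 90% or 94.5%, the pooled test rejects in 29–97%. That is correct, but no cut-off is specified, so nothing secures that case, and the benign-only test still does better there. The falling-sensitivity row lies outside the planned AUC range (its operating points imply AUCs of about 0.97 and 0.89) and serves only as illustration.

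**Conclusion.** The concern holds. As written, the only named test addresses neither the AUC improvement that sized both parts nor the stated aim of better sensitivity and, above all, specificity. That conclusion follows from the text and the identity in step 2 alone.

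The rejection rates also rest on assumed prevalence, correlation, cut-off and binormal scores, none of which the documents give. Across those assumptions, power for the planned gain runs from 3% to 97% depending on the unstated cut-off and the case mix, and a pure threshold shift is declared significant in 63–85% of trials. A significant result would show only that the positive-call rate changed. This must be corrected before analysis. It does not imply that 120 or 40 patients is the wrong number.

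**What to change.** Replace the first two sentences of section 2.5 with wording such as:

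*Primary analysis: the paired difference in AUC between multiparametric ultrasound and B-mode against histopathology, tested two-sided at 5% with a method for correlated ROC curves (e.g. DeLong), with a 95% confidence interval. Secondary: McNemar tests within histologically malignant lesions (sensitivity) and within histologically benign lesions (specificity), with 95% confidence intervals for the paired differences.*

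This also removes the reference to statistical independence. Before reading starts, fix:

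- one overall suspicion rating for multiparametric ultrasound on the same BI-RADS scale as B-mode, keeping categories below 4a available, because section 2.1 also admits lesions found suspicious clinically or on mammography or MRI;
- one positive cut-off common to both methods;
- how the two radiologists' readings (section 2.4 and the amendment) and several lesions per patient (section 2.3.1.2) enter the analysis, since standard DeLong handles neither.

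In the amendment, state that the same paired AUC test applies, with histological response, defined in advance, as the reference. The sponsor must also name the primary time point and the two classifiers being compared.

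The cost is one overall rating per lesion from the existing readers, plus rules set in advance. Power should be stated honestly. In the model above, the paired AUC test comes near 80% only around r=0.5 with balanced prevalence, or at higher correlation, and a coarse rating scale lowers it. The split McNemar tests reach only 10–40% each at the symmetric effect, which is why they are secondary and reported with intervals.

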2.3.1.2 Image evaluation

Image evaluation of the B-mode ultrasound will be performed according to the revised ACR BI-RADS lexicon for ultrasound 5th edition, (3). Lesions will be evaluated for shape (oval, round or irregular), orientation (parallel or not), margin (circumscribed, microlobulated, indistinct, angular or spiculated), internal echogenicity (anechoic, hyperechoic, isoechoic, hypoechoic, heterogeneous or complex cystic and solid) and posterior acoustic features (none, enhancement, shadowing or combined pattern). Additionally on the coronal plane the presence or absence of retraction will be noted (22). The number and exact size of lesions in all 3 dimensions will be documented. Finally the likelihood of malignancy will be reported according to the ACR BI-RADS lexicon (3), with 4a = low suspicion for malignancy; 4b = moderate suspicion for malignancy; 4c = high suspicion for malignancy and 5 = highly suggestive of malignancy.

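### The only named test compares how often each method calls a lesion positive, not how accurate it is, so its p-value cannot show the improvement the study seeks

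*Combined protocol and SAP*

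**What the plan says.** Section 1.2 expects that "an increased sensitivity and especially specificity of US of the breast can be achieved". Section 2 sizes the study at 120 patients for an AUC rising from 0.8 to 0.9, with 5% type I and 20% type II error, and makes histopathology the reference standard.

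Section 2.5 then sets out the analysis in three sentences.

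- The test: McNemar, comparing B-mode alone against B-mode plus "additional ultrasonographic examinations positive and negative results to determine statistical independence". Histology does not appear in this sentence.
- ROC: "ROC analysis will be performed to estimate the overall performance of B-mode ultrasound and multiparametric ultrasound". This is estimation; no test of the AUC difference is named.
- Accuracy: "Using the histopathological data the numbers of true-negative (TN), true-positive (TP), false-negative (FN) and false-positive (FP) results" are obtained, and sensitivity, specificity, accuracy, PPV and NPV are calculated from them. No test or confidence interval is attached.

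Section 2.3.1.2 grades suspicion from 4a upwards, ending with "4c = high suspicion for malignancy and 5 = highly suggestive of malignancy". Nowhere is it stated which grades count as a positive call, for B-mode or for the combined examination.

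The amendment for the 40-patient chemotherapy part adds: "The statistical evaluation will be performed as described in the original study protocol".

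**The concern.** Two things are wrong with the McNemar sentence. First, the hypothesis is misnamed. McNemar tests equality of two paired proportions, and two readings of the same lesion are expected to be dependent. Second, the proportions compared are positive calls over all lesions. Pooling is not stated outright, but it is what the sentence says when followed as written.

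For the stated aim this matters. Better sensitivity means more positives among cancers, and better specificity means fewer positives among benign lesions. In the pooled table the two pull against each other. A non-significant result could hide gains in both. A significant fall in positives could mean fewer false positives or more missed cancers, and the test cannot say which.

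The chemotherapy part inherits the same sentence. All its patients have cancer, so malignancy cannot separate the groups there.

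**Working it through.** **The plan's own figure.** For a paired AUC comparison with Hanley–McNeil variances, N = (1.96 + 0.84)² × [v₁ + v₂ − 2r√(v₁v₂)] / (0.9 − 0.8)², where v₁ and v₂ are the AUC variances multiplied by N. The documents do not give the malignant share, the correlation r or the sidedness. With two-sided 5%, malignant share 30–70% and r from 0 to 0.7, N runs from 338 (30% malignant, r = 0) to 76 (60%, r = 0.7), and is 117 at 60% and r = 0.5. So 120 is attainable and is not disputed. It is, however, the size for a paired AUC test, which Section 2.5 does not name.

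**What the test compares.** With malignant share π, sensitivity Se and specificity Sp, the positive-call rate is π·Se + (1 − π)(1 − Sp). The change between methods is

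D = π·ΔSe − (1 − π)·ΔSp.

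The test as written has D = 0 as its null hypothesis. That holds whenever π·ΔSe = (1 − π)·ΔSp, however large both gains are.

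**Illustrative counts.** Take 60 malignant and 60 benign lesions. The exact p is 2·P(X ≤ min(b, c)), capped at 1, with X binomial(b + c, ½) and b, c the two discordant counts.

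- Ten malignant calls change to positive and ten benign calls change to negative; all 20 changes are improvements. Pooled: 10 against 10, p = 1.00. Within malignant: 10 against 0, p = 2 × 0.5¹⁰ = 0.002. Within benign: the same.
- Fifteen calls change from positive to negative and none the other way. Pooled: p = 2 × 0.5¹⁵ = 0.00006, whether all 15 are benign (specificity better) or all 15 malignant (sensitivity worse).

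**Simulation at N = 120.** Assumptions not in the plan: one lesion per patient, paired binormal scores, correlation within each histology group 0.3–0.6, exact two-sided McNemar, 20,000 trials per setting. The separation is √2·Φ⁻¹(AUC), which is 1.19 at AUC 0.80 and 1.81 at 0.90. A midway cut-off gives Se = Sp = Φ(0.595) = 72% and Φ(0.906) = 82%.

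| Scenario | Se (%) | Sp (%) | D at π = 0.5 (points) | Pooled rejection |
|---|---|---|---|---|
| 1. Balanced gain | 72→82 | 72→82 | 0.5×10 − 0.5×10 = 0 | 2.6–4.4% (40–60% malignant); about 2.6–9% (30–70%) |
| 2. Intermediate | 90→93 | 46→63 | 0.5×3 − 0.5×17 = −7 | 7–60% (30–70%) |
| 3. Specificity gain only | 95→95 | 32→57 | 0 − 0.5×25 = −12.5 | 36–96% (30–70%) |
| 4. No gain (AUC 0.80 for both), stricter cut-off | 72→54 | 72→86 | 0.5×(−18) − 0.5×14 = −16 | 81–94% |

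Scenarios 3 and 4 both reject towards fewer positives, so on the p-value a real improvement and a mere cut-off shift look alike. In scenario 2 at 50% malignant and correlation 0.5, the pooled test has 27% power against 53% in benign lesions alone.

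**Power of the alternatives.**

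- Stratified McNemar, scenario 1: 22% in each stratum at 50% malignant and correlation 0.5 (15–31% over 40–60% malignant, about 10–36% over 30–70%). After Holm: 16% each, 27% for at least one.
- Stratified McNemar, scenario 3, same setting: 86% in the benign stratum, 78% after Holm.
- Paired AUC test (DeLong), scenario 1, 40–60% malignant: 64–84% on continuous scores and 59–77% on a four-level scale cut at quartiles.

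**Chemotherapy part.** With N = 40, AUC 0.70 to 0.90, midway cut-offs and an assumed 20–50% responders, the pooled test rejects in 1.6–14%. Stratified tests reject in 0.2–14% among responders and 14–34% among non-responders.

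**The case against.** **The authors may have meant a stratified test.** Section 2 also uses positive and negative for the histological result, so McNemar within histologically positive and negative lesions is a possible reading. It is not the natural one, because in Section 2.5 the words attach to the ultrasound examinations. If it was the intent, one clause settles it.

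**Accuracy is reported anyway.** The cross-classification against histology would show a reader whether fewer positives meant fewer false positives or missed cancers, so scenarios 3 and 4 would be told apart in the full report. The AUC-based sample size also implies a test of AUC. This stands, and it is why the study remains interpretable. But these are estimates with no interval or named test, and the only planned p-value still addresses a different quantity.

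**The balanced scenario is close to the worst case.** The Introduction cites B-mode sensitivity of 94–95.4% and specificity of 83–87.4%, which leaves little room for a sensitivity gain to cancel anything, and Section 1.2 stresses specificity. This also stands: the loss of power depends on the scenario. The inability to separate removed false positives from missed cancers does not.

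**McNemar on correct versus incorrect calls is another option.** In scenario 1 at 50% malignant and correlation 0.5 it has 46% power against 22% per stratified test, and in scenario 4 at 50% malignant it rejects in only about 4–5%. It is a reasonable addition. But the change in accuracy, π·ΔSe + (1 − π)·ΔSp, depends on case mix. In scenario 4 it is 0.3×(−18) + 0.7×14 = +4.4 points at 30% malignant and 0.7×(−18) + 0.3×14 = −8.4 at 70%, with AUC unchanged. It therefore does not replace separate reporting of sensitivity and specificity.

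**Conclusion.** The concern holds. As written, the one named test has a misnamed hypothesis and compares positive-call rates, so its result cannot show whether sensitivity or specificity improved. The algebra and the illustrative counts need no distributional model. The rejection rates rest on the assumed binormal scores, case mix and correlation: from 2.6–4.4% under a balanced gain at 40–60% malignant, to 36–96% under a specificity-only gain, to 81–94% when only the cut-off moves and AUC does not.

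This should be fixed but is not fatal, because the accuracy measures are still estimated against histology. The missing positivity cut-off and the unnamed AUC test are connected gaps that the same edit can close.

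**What to change.** In Section 2.5:

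1. Apply McNemar separately in histologically malignant lesions (sensitivity) and histologically benign lesions (specificity). Give the purpose as testing those paired differences, in place of independence.
2. Report each paired difference with a 95% confidence interval, and state a multiplicity rule such as Holm.
3. State in advance, for each method, which grades or findings make a call positive.
4. Name a paired test of the AUC difference with its confidence interval, for example DeLong, since the 120 patients were justified on AUC. Let this comparison and the intervals carry the interpretation.
5. In the amendment, state that histologic response replaces malignancy as the stratifier.

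The cost is a few sentences and no new data or patients, but the cut-off must be settled beforehand. The price is modest power: each stratified test uses only its own group. In the 40-patient part the tests are weak enough that estimates with intervals are the realistic output.

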2.4 Evaluation of multiparametric ultrasonographic data

After evaluation of US data for clinical purposes two radiologists blinded to the findings of the other imaging modalities or the histopathological diagnosis, will evaluate the multiparametric US data acquired according to the above mentioned criteria. Results of multiparametric US will be compared to the results of B-mode ultrasound.

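### In the neoadjuvant phase, nothing stops readers from scoring the early scans with the same patient's later ultrasound scans in view, which can inflate the accuracy credited to the early scan

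*Combined protocol and SAP*

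**What the plan says.** The Amendment to the Study Protocol seeks imaging biomarkers that "help to differentiate treatment responders from non-responders immediately after onset of NAC". It adds "an additional mp US examinations on the 3rd day after the 1st cycle", in the hope of an early "prediction of histologic response". Later scans follow: "Patients will be examined again in the week after the 2nd, 4th and 6th (last) cycles of NAC", with one more after cycle 8 where eight cycles are given.

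For the assessment of response, "functional imaging data of the baseline examination and of the examinations after the 1st, 2nd, 4th and 6th (+/- 8th) cycle will be compared" and this is done "by two experienced radiologists independently". No reading order, locking of scores or masking to later scans is given.

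Image analysis and statistics are both carried over from the original protocol. Section 2.4 there specifies "two radiologists blinded to the findings of the other imaging modalities or the histopathological diagnosis". Section 2.5 specifies a McNemar test, ROC analysis and accuracy measures for B-mode against multiparametric ultrasound.

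**The concern.** An early-prediction claim is useful only if it rests on what is available early, namely the baseline and day-3 scans. A scan made after cycle 6 or 8 shows whether the tumour has shrunk, and so carries information about the outcome that the day-3 scan is meant to predict. The masking in section 2.4 was written for a single examination and does not address a series. Reading independently separates the two radiologists from each other, not one time point from the next.

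Several scored items involve judgement: shape and homogeneity on elastography (2.3.2.2), vessel score and morphology (2.3.3.2), and degree of enhancement (2.3.4.2). If a reader scores these on the day-3 scan with the later course in view, the early scan is credited with information from months later. Its apparent accuracy would not carry over to a clinician who has only baseline and day 3.

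**Working it through.** **The plan's own figure.** The Amendment gives 40 patients for AUC 0.7 against 0.9, type I error 5% and type II error 20%. The responder share, the correlation between the two AUCs and the sidedness are not stated, so 40 can be neither confirmed nor refuted. It is reachable. Assume a paired, two-sided comparison, 50% responders, correlation 0.5 and Hanley-McNeil variances. At N = 42 (21 per class) the variances are 0.00660 and 0.00251. The variance of the difference is 0.00660 + 0.00251 − 2 × 0.5 × √(0.00660 × 0.00251) = 0.00504, so the SE is 0.0710. Power is Φ(0.20/0.0710 − 1.96) = 0.80. Across other assumptions (two-sided, paired) the required N runs from 29 to 178. The sample size is not in dispute here.

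**Illustration of look-ahead.** All inputs are assumptions; the documents give none of them.

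- Equal-variance binormal scores, with d′ = √2 × Φ⁻¹(AUC).
- True early AUC 0.70, so d′ = 0.7416.
- Late-scan AUC 0.80 (d′ = 1.1902) or 0.90 (d′ = 1.8124).
- Weight w of the late scan relative to the early evidence: 0.25 or 0.5.
- Within-class correlation ρ between early and late scores: 0 or 0.5.

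The combined score has d′ = (d′_early + w × d′_late) / √(1 + w² + 2wρ), and the apparent AUC is Φ(d′/√2).

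- Late AUC 0.90, ρ = 0, w = 0.5: (0.7416 + 0.9062)/√1.25 = 1.474, AUC 0.851.
- Late AUC 0.90, ρ = 0, w = 0.25: (0.7416 + 0.4531)/√1.0625 = 1.159, AUC 0.794.
- Late AUC 0.80, ρ = 0.5, w = 0.25: (0.7416 + 0.2976)/√1.3125 = 0.907, AUC 0.739.

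| Late AUC | ρ | w = 0.25 | w = 0.5 |
|---|---|---|---|
| 0.90 | 0 | 0.79 | 0.85 |
| 0.90 | 0.5 | 0.77 | 0.81 |
| 0.80 | 0 | 0.76 | 0.80 |
| 0.80 | 0.5 | 0.74 | 0.76 |

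**Effect on a difference between two methods.** Suppose the 0.7 and 0.9 are B-mode and multiparametric AUCs, and both reads take in the same late scan (AUC 0.90, ρ = 0) with the same weight. The second read has early d′ = 1.8124.

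- w = 0.25: (1.8124 + 0.4531)/√1.0625 = 2.198, AUC 0.940. Difference 0.940 − 0.794 = 0.146.
- w = 0.5: (1.8124 + 0.9062)/√1.25 = 2.432, AUC 0.957. Difference 0.957 − 0.851 = 0.106.

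Equal contamination raises both AUCs and shrinks the difference from 0.20.

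**The case against.** The strongest reply is that the Amendment is silent on reading order, and silence is not a procedure. Image analysis follows the original protocol, where an examination is scored on its own criteria, so scoring each scan first and comparing afterwards is a natural reading. This stands in part. A reader might infer that early scans will be scored with the outcome in view, but the text only permits it. It does not exclude it either.

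A reader might also infer that look-ahead leaves the early-prediction objective untested. The documents do not support that as a consequence of reading order. Response is not defined, no time point is attached to the AUC, and the inherited ROC analysis takes carcinoma as the positive result although all 40 patients have cancer. Perfect masking would leave those gaps in place.

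A third tempting inference is that leakage could supply much of the hypothesized gain from 0.7 to 0.9. That fails because the 0.7 is not stated to be the unaided day-3 scan. If the comparison is B-mode against multiparametric ultrasound, equal leakage narrows it. Unequal leakage could act differently.

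Two further points stand. Shear-wave velocity, time to peak and lesion size are measured and less exposed, although placement of the regions of interest can still be influenced. The Amendment also aims to monitor response over the course of treatment, and comparing the full series serves that aim. Finally, it reports only a moderate correlation of ultrasound with final histopathologic tumour size, so a late scan would not fully reveal the outcome.

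**Conclusion.** The concern holds as a gap in the reading procedure. A full-series comparison, under blinding that leaves later ultrasound scans visible, allows look-ahead in the scores meant for early prediction. The quantity at risk is the stand-alone accuracy of the early scan, chiefly on the subjective items.

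The size of the bias cannot be derived from the documents. For a true early AUC of 0.70, the illustration gives an apparent value of about 0.74 to 0.85. It rests on assumed binormal scores, a late AUC of 0.80 to 0.90, a within-class correlation of 0 to 0.5 and a weight of 0.25 to 0.5. No conclusion follows about the planned difference between 0.7 and 0.9. This is an inexpensive improvement that should be made; it does not show that the phase as planned must fail.

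**What to change.** Amend the paragraph on assessment of treatment response along these lines:

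- Each follow-up examination is read against baseline, or against earlier examinations, only.
- Reads are made in chronological order, and each score is locked before the next examination of that patient is opened.
- Readers are masked to later ultrasound examinations and to clinical response. Histology stays masked, as section 2.4 already requires.
- Only the locked day-3 and post-cycle-2 scores enter any ROC analysis of early response against histologic response.
- The full-series comparison is kept as a separate, descriptive read.

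The cost is a short amendment, a read form that locks, and slightly more handling of the reading sessions. Readers, patients and examinations are unchanged. Defining histologic response, and naming the time point and comparator for the AUC, is separate work that this change does not replace.
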